**Methodology:**

This is a Phase 3, double-blind, randomized, placebo-controlled trial of reldesemtiv in patients aged 18 to 80 with ALS. The screening and qualification period for the trial will be no more than 21 days in duration. Approximately 555 eligible ALS patients will be randomized (2:1) to receive the following dose of reldesemtiv or placebo (stratified by riluzole use and edaravone use at baseline) for the first 24 weeks (double-blind placebo-controlled period):

- 300 mg reldesemtiv twice a day for a 600 mg total daily dose (TDD)
- Placebo twice daily

At the end of the 24-week double-blind, placebo-controlled period, patients will transition to the active drug period, where all patients will receive the following dose of reldesemtiv for the next 24 weeks:

- 300 mg reldesemtiv twice a day for a 600 mg TDD for patients who were not down titrated during the 24 weeks of blinded dosing
- 150 mg reldesemtiv twice a day for a 300 mg TDD for patients who were down titrated for any reason during the 24 weeks of blinded dosing

For the entire 48 weeks of dosing, patients and sites shall remain blinded to the randomized treatment assignment patients received during the first 24 weeks.

Study drug should be taken twice daily, morning and afternoon (at least 8 hours apart) and should be taken either with or within the 2-hour period following food.

For patients who complete Week 48 and want to enter the open label extension (OLE), they will not have the follow-up visit; instead, they will enter the OLE on the same day as their Week 48 visit. If the patient does not want to enter the OLE, or if the OLE has not yet been approved at the site, the follow-up visit will take place.

**Number of Subjects (planned and analyzed):** Approximately 740 patients will be screened in order to randomize/enroll approximately 555 patients, such that approximately 444 evaluable patients complete the 24-week of double-blind placebo-controlled period of the trial.

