**Statistical methods:**

Unless otherwise specified, efficacy analyses will be performed on the full analysis set (FAS) by randomized treatment group. The FAS consists of all randomized patients who receive any amount of study drug and have a baseline and at least one post baseline efficacy assessment or have survival status recorded during the 24-week double-blind placebo-controlled period.

The global null hypothesis for the primary endpoint is that there is no treatment difference in the change from baseline to Week 24 in ALSFRS-R total score between patients randomized to placebo and those randomized to reldesemtiv.

The primary analysis will be conducted using a Mixed Model for Repeated Measures (MMRM) with a restricted maximum likelihood method (SAS® PROC MIXED default). The model terms will include treatment group, baseline ALSFRS-R total score, visit, baseline riluzole use, and baseline edaravone use as well as the following interaction terms: baseline ALSFRS-R total score-by-visit and treatment group-by-visit interactions. Other baseline covariates identified by stepwise selection in a regression model will also be included in the primary analysis model if they are key predictor variables for the change from baseline to Week 24 in ALSFRS-R total score based on the blinded data. The regression model used to identify baseline covariates will include pre-study disease progression rate, age and baseline percent predicted FVC as model terms. An unstructured variance-covariance matrix will be used in the primary analysis model.

Prior to applying the MMRM, missing data will be imputed using the multiple imputation procedure (Rubin 1987) for the primary analysis, and the estimates from each imputed dataset will be combined into one set of overall estimates using the SAS® PROC MIANALYZE procedure. The extent of missing data and the pattern of missing data reasons will be tabulated. Least square means (LSM), LSM difference and the corresponding standard errors, 95% confidence intervals (CI) and p-values will be presented. Multiplicity will be addressed using closed testing procedure detailed in [Section 8.5](#).

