### 4.3. Sample Size Considerations

#### 4.3.1. Sample Size Justifications

With a 2:1 randomization ratio to reldesemtiv and placebo groups, respectively, an initial sample size of approximately 555 patients is required to achieve at least 90% power to detect a 1.8 point treatment difference between reldesemtiv and placebo in the change from baseline to Week 24 in ALSFRS-R total score. This calculation is based on a two-sample t-test with two-sided alpha at 0.05 level, a common standard deviation of 5.5 points, and accounting for data missing and early treatment termination.

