## 8.5. Multiple Comparisons and Multiplicity

The null hypothesis for the primary and secondary efficacy endpoints will be tested in a prespecified order using a closed testing procedure. This procedure will maintain the family-wise error rate at two-sided significance level of 0.0499 for all primary and secondary hypotheses tested in a confirmatory sense. The testing steps are described as follows:

- Step 1: The null hypothesis for the primary endpoint  $H_{01}$  is that there is no treatment difference in the change from baseline to Week 24 in ALSFRS-R total score between patients randomized to placebo and those randomized to reldesemtiv in the FAS. The hypothesis will be tested at the two-sided significance level of 0.0499. If this hypothesis is rejected, testing will proceed to Step 2; otherwise testing will stop.
- Step 2: The null hypotheses for the first secondary endpoint  $H_{02}$  is that the Mann-Whitney probability of a more favorable status in reldesemtiv or placebo group in the FAS is 0.5. The status is quantified by joint ranks based on the combined assessment of change in ALSFRS-R total score, time to onset of respiratory insufficiency, and survival time up to Week 24. The hypotheses will be tested at the two-sided significance level of 0.05. If this hypothesis is rejected, testing will proceed to Step 3; otherwise testing will stop.
- Step 3: The null hypotheses  $H_{03}$  is that there is no treatment difference in change from baseline to Week 24 in the percent predicted FVC between patients randomized to placebo and those randomized to reldesemtiv in the FAS. The hypotheses will be tested at the two-sided significance level of 0.05. If this hypothesis is rejected, testing will proceed to Step 4; otherwise testing will stop.
- Step 4: The null hypotheses  $H_{04}$  is that there is no treatment difference in change from baseline to Week 24 in the ALSAQ-40 total score between patients randomized to placebo and those randomized to reldesemtiv in the FAS. The hypotheses will be tested at the two-sided significance level of 0.05. If this hypothesis is rejected, testing will proceed to Step 5; otherwise testing will stop.

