## 8.6. Analysis of the Primary Efficacy Endpoint

### 8.6.1. Primary Efficacy Analysis

The primary efficacy endpoint of the trial is the change from baseline to Week 24 in ALSFRS-R total score. The estimand of the primary efficacy endpoint is the difference in the mean changes from baseline to Week 24 in ALSFRS-R total score between patients randomized to placebo and those randomized to reldesemtiv in the FAS.

The analysis for the primary efficacy endpoint will be conducted using a mixed model for repeated measures (MMRM) based on a restricted maximum likelihood method (SAS® PROC MIXED default). The model terms will include treatment group, baseline ALSFRS-R total score, visit, riluzole use at baseline, edaravone use at baseline as well as baseline-by-visit and treatment group-by-visit interactions. In addition, other baseline covariates identified by stepwise selection in a regression model will also be included in the model if they are key predictor variables for the change from baseline to Week 24 in ALSFRS-R total score. The regression model used to identify baseline covariates will include change from baseline to Week 24 in ALSFRS-R total score as response variable and pre-study disease progression rate, age and baseline percent predicted FVC as model terms. The stepwise selection process with significance at 0.25 level for a variable to be entered to the model and with significance at 0.1 level for a variable to remain in the model will be used. The best-fit model according to AIC will be selected. The evaluation will be performed based on the blinded data before the database lock. An unstructured variance-covariance matrix will be used for the model. Observed data collected up to Week 24 in the FAS will be included in the model.

Prior to applying the MMRM, multiple imputation with fifty invocations under the MAR paradigm will be performed to impute missing data (see [Section 8.6.1.1](#) for imputation method).

Least squares mean (LSM), LSM difference and the corresponding standard error, 95% CI and p-value will be presented. The components used to derive main estimator of the primary analysis are shown in [Table 4](#).

Sensitivity analyses will be conducted to support the robustness of conclusions based on the primary analysis results. See [Section 8.6.2](#) for sensitivity analyses.

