### 1. MMRM for the primary endpoint

```
proc mixed data = artot method = reml;  
  class <usubjid> <visit> <treatment> <baseline riluzole use> <baseline edaravone use>;  
  model <change in ALSFRS-R total score> = <visit> <treatment> <baseline ALSFRS-R total score>  
    <baseline riluzole use> <baseline edaravone use> <visit>*<treatment>  
    <visit>*<baseline ALSFRS-R total score>/ddfm=kr;  
  repeated <visit> / subject = <usubjid> type = un;  
  lsmeans <visit>*<treatment> / pdiff cl;  
run;
```

Note: If the 2nd interim analysis result leads to an increase of the sample size, the final analyses will include the status of being included or excluded from the 2nd interim analysis as a covariate in the model.

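### Covariates selected for predicting Week 24 change enter the primary MMRM without a visit interaction, which may forgo part of their precision gain at Week 24

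*SAP*

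**What the plan says.** The technical summary (Statistical methods) limits the by-visit terms of the primary MMRM to "baseline ALSFRS-R total score-by-visit and treatment group-by-visit interactions". SAP 8.6.1 lists the same two interactions and then states that "other baseline covariates identified by stepwise selection in a regression model will also be included in the model if they are key predictor variables". Table 4 likewise names the selected covariates after the interactions, with no visit term of their own. Candidates are pre-study progression rate, age and baseline percent predicted FVC. The selection regression has a single response, the change at Week 24, and the covariance of the MMRM is unstructured.

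The prototype code in SAP 12.5 item 1 ends its fixed effects with "<visit>*<baseline ALSFRS-R total score>/ddfm=kr". It crosses visit with treatment and baseline ALSFRS-R only, and does not show the selected covariates at all.

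The sample size (SAP 4.3.1) is "required to achieve at least 90% power to detect a 1.8 point treatment difference between reldesemtiv and placebo". It is justified as follows: "This calculation is based on a two-sample t-test with two-sided alpha at 0.05 level, a common standard deviation of 5.5 points". No covariate adjustment enters that calculation.

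**The concern.** A covariate without a visit interaction is assumed to shift the change score equally at Week 4 and at Week 24. That is unlikely for progression rate, which the footnote to Figure 4 in Protocol 4.2 defines as points lost per month. Change is zero at baseline, so the effect of a monthly rate would naturally build up over time. The case is less clear for age and FVC.

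Where the true effect grows, the single coefficient is a compromise across visits, and generalised least squares gives most weight to early visits, where variance is small. The Week 24 contrast is then only partly adjusted for variables chosen because they predict Week 24.

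The SAP allows visit-specific effects elsewhere. Baseline ALSFRS-R has its own by-visit term, the subgroup models in 8.4.1 add subgroup-by-visit terms for groupings of these same three variables, and the sequential imputation in 8.6.1.1 fits each visit separately. No reason is given for treating the selected covariates differently. What is at stake is precision on the primary test, which also gates every secondary test in SAP 8.5.

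**Working it through.** **Inputs from the documents.** Difference 1.8, SD 5.5, two-sided alpha 0.05, power 90%, allocation 2:1 (SAP 4.3.1); 555 randomized and 444 evaluable (technical summary), an implied loss of 20%. Phase 2: 0.9 points at Week 12, p = 0.01 (taken as two-sided), 458 patients in four equal arms with the three active arms pooled (Protocol 4.2).

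**Assumptions not in the documents.** R², the share of Week 24 variance explained by the covariates given baseline ALSFRS-R, at 5%, 10% and 20%, applied to SD 5.5; the time profile of the covariate effect; and the within-patient covariance.

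**1. Plan's own figure.** Placebo n = 1.5 × (1.960 + 1.282)² × 5.5² / 1.8² = 147.2, so 148. The total is 3 × 148 = 444, and 444 / 0.80 = 555. The standard error is 5.5 × √(1/148 + 1/296) = 0.554, so power = Φ(1.8/0.554 − 1.960) = 0.902. The plan's figure is reproduced with no covariate.

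**2. How fast variance grows.** Phase 2 implies SE = 0.9/2.576 = 0.349 and a Week 12 SD of 0.349 / √(1/343.5 + 1/114.5) = 3.24 (2.98 to 3.43 over the rounding of p). With a random slope plus independent error, and SD 5.5 at Week 24, error variance = (3.24² − 5.5²/4)/0.75 = 3.9. The error SD is 1.97 (1.32 to 2.36), and I use 2. This treats the Phase 2 model-based SE as a simple two-group SE, and that population was broader.

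**3. The common coefficient.** Let b hold the visit-specific coefficients and S the working covariance, including the misfit, solved as a fixed point. Then g = (1′S⁻¹b)/(1′S⁻¹1). The share of the Week 24 variance gain kept is 1 − (1 − g/b₂₄)².

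Example, effect linear from zero, R² = 10%: b₂₄ = 5.5 × √0.10 = 1.739 and g = 0.153 × 1.739 = 0.266. Week 24 residual variance is 27.225 + (1.739 − 0.266)² = 29.39 with one coefficient, 27.225 with a by-visit term, and 30.25 unadjusted. Kept: (30.25 − 29.39)/(30.25 − 27.225) = 28%.

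**4. Base case** (linear from zero, random slope plus error SD 2, 148/296 patients):

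| R² | g/b₂₄ | Gain kept | SD, one coefficient | SD, by visit | Power, one coefficient | Power, by visit |
|---|---|---|---|---|---|---|
| 5% | 0.146 | 27% | 5.463 | 5.361 | 0.9054 | 0.9155 |
| 10% | 0.153 | 28% | 5.422 | 5.218 | 0.9095 | 0.9288 |
| 20% | 0.169 | 31% | 5.327 | 4.919 | 0.9187 | 0.9530 |

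Power forgone is 1.0, 1.9 and 3.4 points. Testing at 0.0499, the level set in SAP 8.5, changes power by 0.0002 or less. Simulated complete-data trials with error SD 2 kept 29% at R² 10% and 31% at 20%. Mean estimates were 1.78 to 1.82 across the scenarios simulated, for a true 1.8, and model SEs matched empirical SEs.

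**5. Range** (error SD 1 to 3; random slope, Brownian, or an equal mix):

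| Time profile of effect | Gain lost |
|---|---|
| Linear from zero | 38% to 92% |
| Linear, with 25% of the Week 24 effect already at time zero | 21% to 52% |
| Square root | 17% to 41% |
| Constant | none |
| Quadratic | 63% or more; can be less precise than no covariate |

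**The case against.** The strongest reply is that nothing here is invalid and nothing promised is missing. The estimate is unbiased, its standard error is right, and 90% power was claimed for an unadjusted comparison. In the base case the planned model is above 90% at every R². This stands in full. A reader might infer that a trial sized almost exactly at 90% is short of power because of this choice. The documents do not support that, since any covariate gain is additional to the design.

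A reader might also infer that most of the gain is certainly lost. No section gives an R², a time profile or a within-patient covariance. A square-root profile, or an effect a quarter present at time zero, generally keeps about half or more. Growth from zero is well motivated only for progression rate. That variable is itself computed from baseline ALSFRS-R, already in the model, and Protocol 4.2 restricts entry of slow progressors. Both could reduce its added R², so the 20% row may be optimistic.

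Two smaller points also stand. The code in SAP 12.5 is a prototype that omits the selected covariates, so it cannot show how they enter; the reading rests on 8.6.1, Table 4 and the technical summary. And stepwise selection may retain none of the three, which would make the point moot. The calculation also assumes complete data and does not model the imputation step.

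None of this supplies a reason to prefer a single coefficient. No listed sensitivity analysis recovers the gain either: Estimator 1 reuses the same MMRM, and the Week 24 ANCOVAs in Estimators 2 to 6 leave the selected covariates out.

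**Conclusion.** The point holds as an efficiency improvement. As written, covariates chosen for Week 24 get one coefficient for all visits, and if their effect grows over time part of the Week 24 gain is given up. About 70% is lost under linear growth from zero with random slope plus error SD 2, which amounts to roughly 1, 2 and 3.5 power points at R² of 5%, 10% and 20%. The loss falls to nothing if the effect is constant. I am confident of the mechanism and of how the text reads, but only moderately confident of the size, because R², profile and covariance are all assumed. There is no bias, no invalid standard error and no shortfall against the stated power.

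**What to change.** Before the blinded covariate selection, add a covariate-by-visit interaction for each selected covariate, alongside the existing baseline-by-visit term, in SAP 8.6.1, Table 4, the technical summary and the model statement in 12.5 item 1. The code should also show the selected covariates themselves. The protocol (9.4.2) leaves these extra covariates to the SAP and does not specify whether they are crossed with visit.

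The cost is a short edit in four places and about five degrees of freedom per covariate (six visits less one), negligible with 444 evaluable patients. If the effects prove constant over visits, almost nothing is lost.

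By-visit terms for riluzole and edaravone use are optional and not part of this point. No gain has been calculated for them, and the protocol's listed model includes them without a visit interaction.

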**Table 4: Components of the Main Estimator and Analytical Approach for the Primary Efficacy Endpoint**

Estimator	Attribute				Analytical Approach
	Population	Variable	Intercurrent event	Population-level summary	
Main Estimator	FAS	Change from baseline to Week 24 in ALSFRS-R total score	ALSFRS-R total score collected up to Week 24 will be included in the MMRM. Missing data will be imputed using the method described in Section 8.6.1.1 .	Difference in variable means between reldesemtiv and placebo groups	MMRM based on a restricted maximum likelihood method (SAS® PROC MIXED default). The model terms will include treatment group, baseline ALSFRS-R total score, visit, riluzole use at baseline, edaravone use at baseline as well as baseline-by-visit and treatment group-by-visit interactions and other baseline covariates identified by stepwise selection.

### **8.6.1.1. Imputation of the Missing Data for the Primary Efficacy Analysis**

The extent of missing data and the pattern of missing data reasons will be tabulated. Missing ALSFRS-R total score will be imputed for the primary efficacy analysis described in [Section 8.6.1](#). For each randomized treatment group, the missing data will be filled sequentially starting at the earliest time point and progressing until the last time point based on a multivariate joint normal imputation model ([Schafer 1997](#)). The imputation model will include the following terms: ALSFRS-R total score at previous visits including baseline (in reldesemtiv or placebo group), riluzole use and/or edaravone use at baseline, and other covariates selected using stepwise regression for the primary analysis (see [Section 8.6.1](#)) such as pre-study disease progression rate, age and/or baseline percent predicted FVC. Fifty set of complete data will be generated for analysis to produce 50 sets of estimates. Rubin's imputation rules ([Rubin 1987](#)) will be used to combine the LSM estimates of the treatment difference, 95% confidence interval and p-value. The example SAS code can be found in [Section 12.5](#).

### **8.6.2. Sensitivity Analyses of the Primary Efficacy Endpoint**

Sensitivity analyses for the primary efficacy endpoint will be conducted based on the FAS and with the common outcome variable and population-level summary. The outcome variable is change from baseline to Week 24 in ALSFRS-R total score, and the population-level summary is the difference of the variable means between reldesemtiv and placebo groups. The sensitivity estimators and the corresponding approach for handling intercurrent events, imputation method and analytical method are shown in [Table 5](#).

In addition, analysis of the primary endpoint will be conducted for the subgroups listed below to evaluate consistency of the observed treatment effect. Same analysis method as described in [Section 8.6.1](#) will be applied to support the analysis result of the primary endpoint.

- Patients with down titration to 150 mg BID at Week 24 (yes, no)
- Patients with COVID-19 related intercurrent events requiring hospitalization (yes, no)
- Patients with COVID-19 related fatal event (yes, no)

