Patients must interrupt study drug for certain specified laboratory abnormalities. Hepatic related interruptions are permanent discontinuations. For renal related laboratory abnormalities, the interruption continues until the laboratory value in question has returned to the threshold specified in the protocol for re-initiation of treatment. Patients may then resume dosing at 1 table twice a day thereafter (150 mg twice daily). Patients also may be down-titrated to 1 tablet twice a day by the Investigator in the case of adverse events felt to be related to study drug. Once patients have been down-titrated to one tablet twice daily for any reason, their dose may not be returned to two tablets twice daily.

Data Monitoring Committee:

An independent Data Monitoring Committee (DMC) will periodically assess patient safety in an unblinded manner during the course of the trial.

Interim Analyses:

Twelve (12) weeks after approximately one-third or more of the planned sample size is randomized, the first interim analysis may be triggered. Its purpose is to determine if there is a lack of effect of reldesemtiv on the ALSFRS-R in CY 5031, a finding that would be inconsistent with the prior observed effect on the change from baseline at 12 weeks in ALSFRS-R total score in the Phase 2 trial, CY 5022. At this interim analysis, the DMC will receive unblinded efficacy data from the independent, third-party biostatistical group supporting them and assess the effect of reldesemtiv on the change from baseline to Week 12 in the ALSFRS-R total score. At this interim assessment, if the treatment difference for change from baseline to Week 12 in ALSFRS-R total score has a one-sided p-value larger than or equal to 0.5 (ie, the estimated treatment difference of the change from baseline at Week 12 in ALSFRS-R total score is favoring placebo), the DMC may recommend stopping the trial due to futility. This futility analysis based on the data of change from baseline to Week 12 in ALSFRS-R will not have any alpha spending in the final analysis of the trial. The Sponsor will monitor the blinded aggregate standard deviation of the change from baseline to Week 12 in ALSFRS-R total score periodically and possibly adjust the specified p-value before this interim analysis is conducted.

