6.3. Measures to Minimize Bias: Randomization and Blinding

All patients will be centrally assigned to randomized study drug using an Interactive Web Response System (IWRS). Before the trial is initiated, the log in information & directions for the IWRS will be provided to each site.

Study drug will be dispensed at the study visits summarized in the SoA ([Section 1.3](#)). Returned study drug should not be re-dispensed to the patients.

The IWRS will be programmed with blind-breaking instructions and the unblinding procedure is documented in the IWRS User Manual. In case of an emergency, the investigator has the sole responsibility for determining if unblinding of a patient's treatment assignment is warranted. Patient safety must always be the first consideration in making such a determination. If the investigator decides that unblinding is warranted, the investigator should make every effort to contact Cytokinetics prior to unblinding a patient's treatment assignment unless this could delay emergency treatment of the patient. If a patient's treatment assignment is unblinded, Cytokinetics must be notified within 24 hours after breaking the blind. The date and reason that the blind was broken must be recorded in the source documentation and CRF, as applicable.

An unblinded physician (unmasked to renal labs but blinded to treatment assignments) who is not on the study team may direct a study drug interruption and a down-titration of patients based upon review of unmasked renal function laboratory values that meet the prespecified criteria ([Section 6.6](#) and [Section 7.3](#)). In order to preserve blinding of site staff and the study operation team, a small number of placebo patients will be selected for dummy down-titration during the study by the unblinded Clinical Research Organization (CRO) physician and will undergo repeat laboratory testing similar to what could be directed for patients receiving active treatment with laboratory abnormalities. The blinded down-titration selection criteria and records will be documented by the unblinded physician and the unblinded statistician separately. In order to maintain the blind, placebo patients who had a dummy down-titration during the double-blind dosing period will take 150 mg bid of reldesemtiv during the active drug period.

The randomization treatment assignments for individual patients will remain blinded to site staff and patients until the entire study is completed and the database is locked.

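### SAP 8.6.2 compares arms on the primary endpoint within subgroups formed after randomisation (down-titration, COVID-19 hospitalisation, COVID-19 death) and presents the results as support for the primary effect

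*SAP*

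**What the plan says.** After Table 5 is introduced, SAP 8.6.2 adds that "analysis of the primary endpoint will be conducted for the subgroups listed below to evaluate consistency of the observed treatment effect". Three yes/no splits follow:

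- by dose reduction, worded as "Patients with down titration to 150 mg BID at Week 24 (yes, no"
- by whether a COVID-19 event led to hospital admission
- by death from COVID-19, worded as "Patients with COVID-19 related fatal event (yes, no"

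The method is that of SAP 8.6.1, and it "will be applied to support the analysis result of the primary endpoint". In 8.6.1, "The model terms will include treatment group, baseline ALSFRS-R total score, visit, riluzole use at baseline" and further terms, so each stratum yields a treatment contrast. Section 8.6.2 does not caution that these contrasts lie outside the randomisation.

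The routes into down-titration are described elsewhere. Protocol 7.3 allows a restart at half dose after a renal hold. The Protocol synopsis adds: "Patients also may be down-titrated to 1 tablet twice a day by the Investigator in the case of adverse events felt to be related". For blinding, Protocol 6.3 says that "a small number of placebo patients will be selected for dummy down-titration during the study"; the SAP's technical summary (reference therapy) describes that selection as random.

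**The concern.** Every other subgroup listed for the primary endpoint (SAP 8.4.1) is a baseline characteristic, and SAP 8.4.2 looks for effect modifiers only among baseline characteristics. The three splits in 8.6.2 depart from that practice. Membership is settled during treatment, so the arms within a stratum need not be alike even if the drug does nothing.

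For down-titration, the documents themselves supply a reason to expect imbalance. Protocol 4.3 reports that falls in cystatin-C eGFR and rises in transaminases were dose related in the Phase 2 trial, and Protocol 2.3.1 lists nausea and fatigue among events that became more frequent with dose. The down-titrated stratum therefore sets patients selected largely by reaction to drug against a group selected partly at random. The remaining stratum loses its susceptible patients mainly from one arm.

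At stake is how the report is read. A favourable result in patients never down-titrated could pass for efficacy at full dose, and a poor result in the others for loss of effect at the lower dose, with no real heterogeneity behind either.

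**Working it through.** **Plan's own figure.** Protocol 9.2: difference 1.8, SD 5.5, two-sided alpha 0.05, 90% power, 2:1 allocation. Placebo n = (1 + 1/2)(1.96 + 1.2816)² × 5.5²/1.8² = 147.2, rounded up to 148. With 296 on reldesemtiv the total is 444, and power is 0.902. The synopsis's 444 evaluable of 555 randomised implies 20% loss, and 444/0.80 = 555. The plan's figure reproduces. The 555 split 370 to 185.

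**Bias in the down-titration strata when the true effect is zero.** Assumptions, none of them stated in the documents:

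- A share p of reldesemtiv patients is down-titrated, 5% to 20%.
- These patients decline x points more than reldesemtiv patients not down-titrated, 1 to 3, for reasons unrelated to efficacy.
- The same liability exists on placebo, but placebo entry to the stratum is unrelated to it.

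Take the mean of patients without the liability as 0. On reldesemtiv, the down-titrated mean is -x and the rest average 0. On placebo, both strata average -xp. The differences, reldesemtiv minus placebo (negative favours placebo), are:

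- down-titrated: -x + xp = -x(1 - p)
- not down-titrated: 0 + xp = +xp

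| p | x | Down-titrated | Not down-titrated |
|---|---|---|---|
| 5% | 1 | -0.95 | +0.05 |
| 5% | 3 | -2.85 | +0.15 |
| 10% | 2 | -1.80 | +0.20 |
| 20% | 1 | -0.80 | +0.20 |
| 20% | 3 | -2.40 | +0.60 |

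The two biases have opposite signs. Both vanish at x = 0, and both reverse if down-titrated patients decline less than the others.

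**False-positive rate.** Simulation under zero effect: 4,000 runs, 370 v 185 patients, total SD 5.5, t-test at 0.05, down-titration of 5/5%, 10/5% or 20/10% (reldesemtiv/placebo).

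| Gap x | Down-titrated | Not down-titrated | Whole population |
|---|---|---|---|
| 0 | 0.047 to 0.052 | 0.047 to 0.054 | 0.050 to 0.052 |
| 2 to 3 | 0.13 to 0.40 | 0.05 to 0.21 | 0.046 to 0.053 |

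**Precision.** SE = 5.5 × √(1/n₁ + 1/n₂); half-width of the 95% interval = 1.96 × SE. All shares are assumed.

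| Stratum | Share, reldesemtiv/placebo | Patients | Half-width |
|---|---|---|---|
| Down-titrated | 5/2% | 18.5 v 3.7 | 6.1 |
| Down-titrated | 10/5% | 37 v 9.25 | 4.0 |
| Down-titrated | 20/10% | 74 v 18.5 | 2.8 |
| COVID-19 event | 2/2% | 7.4 v 3.7 | 6.9 |
| COVID-19 event | 1/1% | 3.7 v 1.85 | 9.7 |

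Power for 1.8 points in the three down-titrated rows is 8%, 14% and 24%.

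**COVID-19 strata.** A patient who dies before Week 24 has no Week 24 ALSFRS-R score, so any Week 24 contrast among such patients rests on the imputation in SAP 8.6.1.1. There is also a practical problem. Six post-baseline visits (Weeks 4 to 24) with an unstructured matrix need 6 × 7/2 = 21 covariance parameters. SAP 8.4.1 has an ANCOVA fallback for non-convergence; 8.6.2 states none for these splits.

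**The case against.** The strongest reply is that nothing confirmatory depends on these analyses. They lie outside the testing sequence in SAP 8.5 and supplement the Table 5 estimators. That stands. A reader might infer that the primary result or its error rate is compromised; the documents do not support that.

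Second, the size of the bias is assumed. The routes to down-titration are narrow: hepatic interruptions are permanent discontinuations (Protocol synopsis and 7.4), and Protocol 6.6 encourages resumption at the full tablet count after an adverse-event interruption. The rate may be low. The down-titrated stratum would then be too imprecise to support a claim, and the bias in the other stratum would be small. This limits the harm, but it also removes the reason for estimating an effect there.

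Third, it is tempting to say that placebo patients enter mostly by dummy selection, so that the stratum carries the whole prognostic gap. The Protocol speaks only of a small number, and a blinded investigator can down-titrate a placebo patient for an adverse event. If placebo entry is partly driven by adverse events, the bias is smaller than tabulated.

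Fourth, the argument about different causes by arm does not extend to COVID-19. Nothing in the documents suggests that reldesemtiv affects COVID-19 hospitalisation or death. Imputing scores after death is not peculiar to that stratum either: the main estimator does it, and Sensitivity Estimator 4 stresses it. What remains is that these strata are post-randomisation, probably very small and, for fatal events before Week 24, without observed Week 24 scores.

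**Conclusion.** The point holds as one of interpretation. SAP 8.6.2 would produce between-arm estimates in strata formed after randomisation and call them consistency and support, with no caveat there or elsewhere. For down-titration, bias is plausible on the documents' own account of how patients enter. Under the stated assumptions (p of 5% to 20%, x of 1 to 3 points, placebo entry unrelated to prognosis) it runs from -0.8 to -2.85 points among the down-titrated and from +0.05 to +0.6 among the rest, against a target of 1.8. The direction is itself an assumption. For the COVID-19 strata the case rests on sparse data and imputed scores, with no documented drug-related mechanism.

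The label of the first subgroup is also unclear. Placebo patients take no 150 mg dose in the blinded 24 weeks, so it could mean a reduced tablet count by Week 24 or the dose on entering the active drug period. Both readings are post-randomisation.

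**What to change.** In SAP 8.6.2:

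1. Remove the between-arm model estimates and p-values for the three subgroups, and the wording that they assess consistency or support the primary result.
2. Report ALSFRS-R outcomes in these strata descriptively by arm, labelled as non-randomised.
3. Point to the whole-FAS analyses already planned. The main estimator (8.6.1 and Table 4) keeps scores collected after down-titration, and Sensitivity Estimator 6 addresses COVID-19 events with both randomised arms intact.
4. Define the down-titration subgroup for both arms, including the treatment of dummy reductions and the time by which the reduction must have occurred.

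An extra estimator that sets scores after down-titration to missing and imputes them is optional. It would answer a different, hypothetical question, discard observed data and rest on an untestable missing-at-random assumption, so it is not part of the required change.

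The cost is one edited bullet list and the loss of a non-confirmatory subgroup estimate. Sample size, alpha and the primary model do not change.
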